Three protocol changes are proposed in this substantial amendment to (a) expand the inclusion criteria to allow enrolment also of patients in hospital with COVID-19 but not yet requiring supplemental oxygen, and (b) allow a minor temporary temperature excursion in the storage conditions of the IMP to facilitate transport from the manufacturer to the clinical site or from the clinical site pharmacy to the bedside, and (c) to raise the exclusionary level for methaemoglobin to >2%.

During the peak of the first wave of COVID-19, there was a sharp influx of patients to hospitals and the vast majority of admissions were at WHO grade 4 and above – i.e. those in need of supplemental oxygen, or intensive care. More recently however, as the hospital numbers have fallen, less severely ill patients have been admitted to hospital, with a significant proportion now being at WHO grade 3. This amendment is proposed to allow the recruitment of grade 3 as well as grade 4 patients, reflective of the changing hospital admissions pattern. Treating patients earlier in the onset of the disease should help patients and reduce the burden on Intensive Therapy Units and respiratory wards.

The storage conditions for the IMP as outlined in the IMPD state that RESP301 must be stored below 25°C (range 15-25°C). On two occasions during transport of the IMP there has been a slight temperature excursion; the first occasion was during transport of the IMP from the manufacturer to the hospital pharmacy when the temperature rose to 25.4°C. The second

occasion was during transport from the hospital pharmacy to the ward and the temperature rose to 25.0°C. On both occasions the protocol conditions were followed and the manufacturer was contacted and permission given to proceed. However, on the second occasion the delay resulted in the patient not receiving the scheduled dose. The IMP has been on stability testing at 40°C and 75% relative humidity and has remained completely stable for 3 months under these conditions. We do not wish to amend the overall storage conditions but request an amendment to allow for short-term temperature excursions up to 30°C for less than 1 hour while the IMP is in transit.

Whereas the normal range for methaemoglobin (mHb) is <1%, this does not take account of the role of comorbidities that might affect the mHb level. Comorbid disorders that impair oxygen transport, such as cardiac and respiratory conditions, can exacerbate a low level mHb (Groeper K et al South Med J 2003;96:504-509). Symptomatic low-grade methaemoglobinaemia is associated with certain treatments for pneumonia, chronic obstructive pulmonary disease and heart disease (Dunford LM et al. Biol Blood Marrow Transplant 2006;12:241-242, Skold A et al. South Med J 2011;104:757-761). Since many of the patients admitted to hospital with COVID-19 may also have comorbidities that could affect the mHb level it is proposed that the exclusion level for mHb be raised to >2%.

A number of non-substantial amendments were also made and are included in the table below.

Section # and Name	Description of Change	Brief Rationale
Substantial Amendment 1		
Title; 1.1; 4.1	Change of Title to include 'WHO grade 3 & 4;	See above
1.1 Primary Endpoint Also Section 3. 9.4.2	Previously measured progression of level 4 patients to > 4 ; now considers progression "by at least one level higher".	To handle grade 3 entrants, as well as grade 4, to the study. See above
1.1 Secondary Endpoint Also Section 3 9.4.3	Amend secondary endpoints to measure time to change in WHO grade for those in level 3, as well as those in level 4.	See above
Throughout	Change of wording to refer to use of supplemental oxygen 'if applicable'.	WHO grade 3 do not require supplemental oxygen, so not all study patients will be using supplemental oxygen.

Section # and Name	Description of Change	Brief Rationale
9.1 , 9.2,	Previous target was level 5 from level 4; now amended to ‘at least one level’ to handle the participants who enter at level 3.	
Substantial Amendment 2		
6.2.2	Addition of text to permit temperature excursions no longer than 1 hour.	See above
Substantial Amendment 3		
2.2.1 5.3, 13	Amendment of Methb threshold from 1% to 2%	See above
Non-substantial amendments		
1.3 Schedule of Activities	Changed description of oxygen measurements pre/post treatment to make clearer and remove repetition.	Instructions were repetitive and unnecessarily confusing
1.3 Schedule of Activities. Footnote 6f	Correction of 5 to 20, to match text elsewhere in document.	Correcting typo error
5.3 Point 2	Amend requirement to receive nebulization from 4 minutes to 8 minutes	4 minutes was an error; 8 mins is expected length of treatment.
6.2.1 et alia 6.4, 8.1.2	Change of ‘medical supervision’ to ‘clinical supervision’, and ;a physician’ to ‘the clinical team’.	As monitoring does not require a doctor.
6.2.2	Addition of text to permit temperature excursions no longer than 1 hour.	See above
7.1	Remove reference to direct bilirubin, since this is no longer to be measured.	
7.1	Remove wording ‘non invasive or’	Study intervention to be discontinued only if invasive ventilation is required.
8	Maximum amount of blood updated to reflect volume and number of tests	
8.2.2	Sentence regarding vital signs removed as duplicate of previous text in the section	

Section # and Name	Description of Change	Brief Rationale
10.3	Remove unnecessary bloodtests: Bicarbonate/CO ₂ ; Serum Glutamic-Oxaloacetic Transaminase ; Serum Glutamic-Pyruvic Transaminase ; direct bilirubin	

Amendment 2.0 (10-Jun-2020)

This amendment is considered to be substantial based on the criteria set forth in Article 10(a) of Directive 2001/20/EC of the European Parliament and the Council of the EU.

Overall Rationale for the Amendment:

The protocol was updated to clarify that staggered dosing is required for all participants treated before completion of the first Independent Data Monitoring Committee (IDMC) review, and to clarify exclusionary criteria and monitoring of methemoglobin (mHb). Information was added to ensure that investigators are aware of the potential risk of interaction between nitric oxide (NO) and other NO donor agents. Other changes, with brief rationale, are summarized in the following table.

Section # and Name	Description of Change	Brief Rationale
Section 1.3 Schedule of Activities (SoA)	Footnote 4 updated to include mHb assessment at the same time points as hematology and clinical chemistry assessments.	For monitoring and assessment of mHb against the discontinuation criteria.
Section 2.2.1 Risk Assessment	Table 2-1 updated to include exclusionary mHb >1%.	The normal reference range for mHb is 0-1% (Longo et al, 2011).
Section 5.3 Exclusion criteria	Exclusion criterion 13 updated to specify that mHb >1% is exclusionary.	

Section # and Name	Description of Change	Brief Rationale

1.1 Synopsis

Protocol Title: An open-label, adaptive randomized, controlled multicenter study to evaluate the efficacy and safety of RESP301 plus standard of care (SOC) compared to SOC alone in hospitalized participants with COVID-19 WHO grade 3 & 4 (NOCoV2)

Sponsor Protocol No.: RESP301-002

Study Phase: Phase 2/Phase 3

Sponsor: Thirty Respiratory Limited

Rationale:

This is an open-label, randomized, multicenter, parallel group, concurrent, controlled study using a sequential adaptive design. Participants will be consented and randomized 2:1 to the Investigational arm or the Control arm. Participants randomized to the Investigational arm will receive inhaled RESP301 (6 mL) administered using a nebulizer 3 times a day (TID) for up to 10 days in addition to the standard of care (SOC) while participants in the Control arm will receive SOC alone.

Objectives and Endpoints:

Objectives	Endpoints
Primary	

To evaluate efficacy of RESP301 in preventing progression of hospitalized COVID-19 participants at level 3 or 4 in the modified World Health Organization (WHO) ordinal scale into higher levels	
Proportion of participants who progress by at least one level higher on the modified WHO ordinal scale by Day 14
Key Secondary	

To assess the effect of RESP301 as measured by room air SpO₂	
Change in room air SpO₂ from baseline over time

To assess the effect of RESP301 as measured by the National Early Warning Score (NEWS) 2 symptom score	
Change in NEWS 2 symptom score from baseline over time

Objectives	Endpoints

 • To assess the treatment response on clinical status 	
 • Change from baseline on the modified WHO ordinal scale at each visit up to Day 28 • Time to improvement of at least one level lower on the modified WHO ordinal scale • Time to progression of at least one level higher on the modified WHO ordinal scale
Additional Secondary	

 • To assess the treatment response on clinical status 	
 • Time to hospital discharge • Incidence of mortality by Day 28
Safety	

 • To assess the overall safety profile of RESP301 in COVID-19 participants 	
 • Clinical safety laboratory measurements • Physical examinations • Vital signs • Concomitant medications • Counts and cumulative incidence of: 
 ○ Adverse events (AEs) ○ Serious adverse events (SAEs) ○ Severe AEs

 • To assess the ability of participants to tolerate nebulization 	
 • Incidence of participants unable to tolerate nebulization due to: 
 ○ Reduction in SpO₂ to < 90%, unless well clinically tolerated according to Investigator's opinion ○ Other clinical signs of intolerance according to Investigator's opinion • Incidence of clinical bronchial hyper-responsiveness related to nebulization
Exploratory	

 • CCI [REDACTED] • CCI [REDACTED] 	

Overall Design:

- Open-label, randomized, multicenter, parallel group, concurrent, controlled study using a sequential adaptive design to evaluate the efficacy and safety of RESP301 added to standard of care (SOC) in hospitalized patients with COVID-19 WHO ordinal scale grade 3 & 4.
- Participants will be stratified by country and presence of risk factors for severe outcomes of COVID-19, based on comorbidities and age as detailed in Section 6.3.
- The study treatment will be permanently discontinued prior to 10 days if the participant:
 - Improves to level 1 or 2 of the modified WHO ordinal scale;
 - Progresses to a level > 4 of the modified WHO ordinal scale;
 - Experiences an event that requires permanent discontinuation as described in Section 7.1.
- An Independent Data Monitoring Committee (IDMC) will be responsible for closely reviewing the safety and efficacy data from interim analyses and for providing their recommendations on continuation of the study. The IDMC will meet after 10, 20, 60 and 150 participants have completed the study (see Sections 9.5 and 9.6).
- A staggered dosing approach will be used for the first 10 participants (up to the first IDMC safety review). Each RESP301 dose will be administered by intermittent inhalation to monitor the tolerability and response to RESP301 (see Sections 6.1 and 9.6).

Disclosure Statement: This is a parallel group treatment study with two arms that are open-label.

Number of Participants:

Approximately 300 adult (male or female) participants will be randomly assigned to study intervention (200 to the Investigational arm and 100 to the Control arm).

Intervention Groups and Duration:

The total study duration for a participant from screening to last follow up will be up to 30 days (± 2 days). The study will be divided into the following periods:

[figure not shown]
- Screening period: starts up to 2 days (48 hours) prior to and extends up to the day of treatment initiation (Day 1); Days -2, -1 and 1
- Intervention period: up to 10 days; Day 1 to Day 10
- Efficacy follow-up: Day 14 and Day 28 (both ± 2 days)
- Safety follow-up: 28 days after treatment initiation; with the participant being contacted by phone call, if not still hospitalized, on Day 28 (± 2 days)

Participants will be consented and randomized 2:1 to the Investigational arm or the Control arm. Participants randomized to the Investigational arm will receive inhaled RESP301 (6 mL) administered using a nebulizer TID for up to 10 days in addition to the SOC, while participants in the Control arm will receive SOC alone.

Data Monitoring Committee: Yes

1.2 Schema

Figure 1–1: Study Design

1.3 Schedule of Activities (SoA)

Table 1-1 Schedule of Activities (SoA)

Procedure	Screening (up to 48 hours before Day 1 ¹)	Intervention Period			Early withdrawal	Efficacy follow-up (Day 14) ² (± 2 days)	EoS efficacy and safety follow-up (Day 28) ² (± 2 days)	Notes
		Day 1 ¹	Daily while hospitalized	Day 10 / hospital discharge				
Informed consent	X							Optional tokenization ICF to be provided for a subset of participants in the United States (see Section 8.4)
Confirmation of COVID-19 infection by nasopharyngeal RT-PCR ³	X							
Inclusion and exclusion criteria	X	X						Recheck clinical status before 1st dose of study intervention
Demographics	X							
Physical examination including height and weight	X			X	X		X ²	Full physical exam and height only at screening

Procedure	Screening (up to 48 hours before Day 1 ¹)	Intervention Period			Early withdrawal	Efficacy follow-up (Day 14) ² (± 2 days)	EoS efficacy and safety follow-up (Day 28) ² (± 2 days)	Notes
		Day 1 ¹	Daily while hospitalized	Day 10 / hospital discharge				
Pregnancy test (urine)	X							All women, including women of childbearing potential and pregnant women, may be enrolled in the study. Pregnancy status should be recorded (see Section 8.3.5). Note: Only females of child bearing potential and pregnant females need to undergo a screening pregnancy test.
Medical history (includes substance usage)	X							History of substance usage or abuse to be recorded but is not exclusionary
Medication history	X							In the prior 3 months
Laboratory assessments (including liver chemistries) ⁴	X ⁴	X ⁴	X (Days 3 and 7 only) ⁴	X ⁴	X ⁴		X ^{2,4}	
12-lead ECG	X							After resting supine for approximately 5 minutes. QRS, QT, QTcF, PR, RR, rate
Vital signs ⁵	X	X	X ⁵	X	X		X	Within 15 minutes prior to study intervention administration

Procedure	Screening (up to 48 hours before Day 1 ¹)	Intervention Period			Early withdrawal	Efficacy follow-up (Day 14) ² (± 2 days)	EoS efficacy and safety follow-up (Day 28) ² (± 2 days)	Notes
		Day 1 ¹	Daily while hospitalized	Day 10 / hospital discharge				
Randomization		X						
Study intervention, TID ⁶		X	X	X				A staggered dosing approach will be used for the first 10 participants (up to the first IDMC safety review). Each RESP301 dose will be administered by intermittent inhalation to monitor the tolerability and response to RESP301 (see Sections 6.1 and 9.6). Where possible study intervention should be administered at approximately the same times each day At least 6 hours between 2 consecutive doses
AE/SAE review	X	X	X	X	X	X	X	
Concomitant medication review	X	X	X	X	X	X	X	
Pre Treatment oxygen / respiratory assessment ⁷	X	X	X	X				
SpO ₂ on room air (after at least 1 minute) prior to study intervention administration and immediately at the end of nebulization ⁶		X	X	X				See Section 8.1.2

Procedure	Screening (up to 48 hours before Day 1 ¹)	Intervention Period			Early withdrawal	Efficacy follow-up (Day 14) ² (± 2 days)	EoS efficacy and safety follow-up (Day 28) ² (± 2 days)	Notes
		Day 1 ¹	Daily while hospitalized	Day 10 / hospital discharge				
Modified WHO ordinal scale	X	X	X	X		X	X	See Section 8.1.1
NEWS 2 assessment ⁷		X	X	X				Prior to study intervention in the morning. See Section 8.1.3

Abbreviations: AE=adverse event; aPTT= activated partial thromboplastin time; CBC=complete blood count; Chem 7=blood chemistry panel (sodium, potassium, chloride, bicarbonate/CO₂, blood urea nitrogen, creatinine, glucose); CV=cardiovascular; ECG=electrocardiogram; IDMC=Independent Data Monitoring Committee; LFTs=liver function tests; mHb=methemoglobin; PT/INR=prothrombin time/international normalized ratio; RT-PCR=reverse transcription-polymerase chain reaction; SAE=serious adverse event; TID=three times daily.

1. Screening and randomization may be on the same day, providing all eligibility criteria are met.
2. For participants who are already discharged at either the Day 14 or Day 28 (EoS) follow-up, there will be a phone call to check AEs/SAEs, concomitant medications, and modified WHO ordinal scale. At EoS, safety laboratory tests (nitrite and mHb only) and weight will be collected for participants in hospital only.
3. COVID-19 infection must be confirmed and documented in chart with a positive result on a validated test.
4. At Screening: CBC, chem 7, mHb, LFTs, and coagulation (PT/INR, aPTT).
On Day 1, Day 3, Day 7 and Day 10, or early withdrawal: CBC, chem 7 (per SOC), and mHb.
On Day 28: nitrite and mHb (participants in hospital at EoS only).
5. Vital signs: temperature, heart rate, blood pressure, respiratory rate. Vital signs to be repeated as per SOC during treatment period.
6. Study intervention comprises the following procedures which are to be done in order and as quickly as possible:
 - a. Discontinuation of supplemental oxygen administration where applicable *
 - b. Close participant oversight by trained health care professional until SpO₂ is stable on ambient air after one minute at least *
 - c. Recording of SpO₂ * pre-nebulization on ambient air
 - d. Preparation of the admixture of RESP301 (to be done no longer than 5 minutes before administration)*
 - e. Administration of the nebulization via a vibrating mesh nebulizer while monitoring SpO₂ and heart rate (alarms set to 89% and 120 beats / min, or as indicated by the Investigator, for stopping study intervention administration and resuming supplemental oxygen where applicable) * If the participant is unable to tolerate nebulization without supplemental oxygen, nasal oxygen may be administered during nebulization.
 - f. Discontinuation of nebulization 20 minutes after preparation of admixture, or no product left in the device, whichever comes first *
 - g. Recording of SpO₂ * post nebulization on ambient air
 - h. Resuming supplemental oxygen where applicable*
 - i. Participant oversight until SpO₂ is stable *
 - j. Recording of SpO₂ *

* for participants on active treatment arm only
7. Participant remains on supplemental oxygen if applicable, and measurements made of respiratory rate, heart rate and SpO₂ and a record of oxygen flow level including mode (nasal cannula, mask)

2 Introduction

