4.1 Overall Design

This is an open-label, randomized, multicenter, parallel group, concurrent, controlled study in hospitalized participants with COVID-19 (WHO ordinal scale level 3 or 4) using a sequential adaptive design to evaluate the efficacy and safety of RESP301 added to standard of care (SOC). Approximately 300 adult (male and female) participants will be consented and randomized 2:1 to the Investigational arm or the Control arm. Participants randomized to the Investigational arm will receive inhaled RESP301 (6 mL) administered using a vibrating mesh nebulizer TID for up to 10 days in addition to the standard of care (SOC) while participants in the Control arm will receive SOC alone.

The study will be divided into the following periods:

- Screening period: starts up to 2 days (48 hours) prior to and extends up to the day of treatment initiation (Day 1); Days -2, -1 and 1

- Intervention period: up to 10 days; Day 1 to Day 10
- Efficacy follow-up: Day 14 and Day 28 (± 2 days)
- Safety follow-up: 28 days after treatment initiation; with the participant being contacted by phone call, if not still hospitalized, on Day 28 (± 2 days)

After screening, eligible participants will be randomized to either RESP301+SOC or SOC alone on Day 1, and the study treatment will be initiated as applicable (Table 1-1). Screening and randomization may happen on the same day (Day 1).

An individual administration of study intervention will be stopped, and supplemental oxygen resumed if applicable, if threshold limits of SpO₂ 89% or heart rate 120 beats/min (or as indicated by the Investigator) are exceeded (see Section 4.2 and Section 8.1.2). However, the participant may continue with subsequent doses if the Investigator judges that the benefit / risk ratio remains positive. In this case, the instruction to continue should be duly recorded in the participant's hospital file and the subsequent nebulization should be closely monitored.

Inhalation of study intervention should be completed within 20 minutes. A staggered dosing approach will be used for the first 10 participants (and enrolment up to completion of the first IDMC safety review) to monitor tolerability and response to RESP301 (see Sections 6.1 and 9.6).

The study treatment will be permanently discontinued prior to 10 days if the participant:

- Improves to level 1 or 2 of the modified WHO ordinal scale;
- Progresses to a level > 4 of the modified WHO ordinal scale;

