8.1 Efficacy Assessments

8.1.1 Modified WHO Ordinal Scale

A modified WHO ordinal scale will be used for consistency with the recent study of lopinavir-ritonavir in adults hospitalized with severe COVID-19 (Cao et al, 2020), to record the participant's status at the time of assessment. The modified WHO ordinal scale includes the following levels:

1. Not hospitalized, no limitations on activities;
2. Not hospitalized, limitation on activities;
3. Hospitalized, not requiring supplemental oxygen;

4. Hospitalized, requiring supplemental oxygen;
5. Hospitalized, on non-invasive ventilation or high-flow oxygen devices;
6. Hospitalized, on invasive mechanical ventilation or extra corporeal membrane oxygenation (ECMO);
7. Death.

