9.4.2 Primary Endpoint

The primary endpoint is the proportion of participants who progress by at least one level higher on the modified WHO ordinal scale by Day 14.

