10.4.1 Definition of AE

AE Definition

• An AE is any untoward medical occurrence in a patient or clinical study participant, temporally associated with the use of a study intervention, whether or not considered related to the study intervention.• NOTE: An AE can therefore be any unfavorable and unintended sign (including an abnormal laboratory finding), symptom, or disease (new or exacerbated) temporally associated with the use of a study intervention.

Events Meeting the AE Definition

• Any abnormal laboratory test results (hematology, clinical chemistry, or urinalysis) or other safety assessments (e.g., ECG, radiological scans, vital signs measurements), including those that worsen from baseline, considered clinically significant in the medical and scientific judgment of the Investigator (e.g., not related to progression of underlying disease).• Exacerbation of a chronic or intermittent pre-existing condition including either an increase in frequency and/or intensity of the condition.• New conditions detected or diagnosed after study intervention administration even though it may have been present before the start of the study.• Signs, symptoms, or the clinical sequelae of a suspected drug-drug interaction.• Signs, symptoms, or the clinical sequelae of a suspected overdose of either study intervention or a concomitant medication. Overdose per se will not be reported as an AE/SAE unless it is an intentional overdose taken with possible suicidal/self-harming intent. Such overdoses should be reported regardless of sequelae.• "Lack of efficacy" or "failure of expected pharmacological action" per se will not be reported as an AE or SAE. Such instances will be captured in the efficacy assessments. However, the signs, symptoms, and/or clinical sequelae resulting from lack of efficacy will be reported as AE or SAE if they fulfill the definition of an AE or SAE.

Events NOT Meeting the AE Definition

- Any clinically significant abnormal laboratory findings or other abnormal safety assessments which are associated with the underlying disease, unless judged by the Investigator to be more severe than expected for the participant's condition.
- The disease/disorder being studied or expected progression, signs, or symptoms of the disease/disorder being studied, unless more severe than expected for the participant's condition.

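### The assessment schedule does not fully capture a primary endpoint defined as any progression by Day 14

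*Protocol*

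**What the plan says.** These are the provisions of the amended protocol, which admits WHO levels 3 and 4.

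- **Endpoint.** Section 9.4.2 defines it as "the proportion of participants who progress by at least one level higher on the modified WHO ordinal scale by Day 14". Section 9.1 makes it a composite of every level above entry. For someone recruited at level 3, a move to supplemental oxygen (level 4) is therefore an event.
- **Schedule.** In Section 1.3 the WHO row is marked at Screening, Day 1, "Daily while hospitalized", Day 10 or discharge, Day 14 and Day 28. The daily column lies under the Intervention Period header, and Section 4.1 fixes that period: "Intervention period: up to 10 days; Day 1 to Day 10".
- **After discharge.** Footnote 2 of the schedule says that at Day 14 and Day 28 "there will be a phone call to check AEs/SAEs, concomitant medications, and modified WHO ordinal scale".
- **What is recorded.** Section 8.1.1 says the scale captures the participant's "status at the time of assessment".
- **Window.** The Day 14 and Day 28 column headings in Section 1.3 each allow ±2 days, so the Day 14 contact can fall anywhere from Day 12 to Day 16.

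**The concern.** An endpoint that counts any worsening up to a date needs either continuous observation to that date or a question that looks back over the gap. As laid out, the schedule gives daily observation to Day 10 and then one reading of current status, taken on a day that can vary by four days. Whether an event is counted can then depend on when contact was made and whether the worsening had already resolved.

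Three kinds of event are exposed:

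- transient worsening on Days 11 to 13, such as a short oxygen need in a level-3 entrant or a short spell of high-flow oxygen in a level-4 entrant;
- readmission after discharge that has resolved before the call, mainly after Day 10 or at a non-study hospital;
- worsening that begins after a Day 12 or Day 13 contact.

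In the other direction, a Day 15 or 16 contact can pick up worsening that began after Day 14. An analysis plan can exclude a dated late event, but it cannot recover a level or date that was never collected.

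**Working it through.** **1. Days without a clearly scheduled inpatient reading.** Daily readings run to Day 10 and the next mark is Day 14. Days 11, 12 and 13 are left: 3/14 = 21% of the risk period. Day 14 is not in the gap, because it has its own contact.

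**2. Effect of the window (14 ± 2).**

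| Contact made on | Days up to 14 left after contact | Days beyond 14 that can enter |
|---|---|---|
| Day 12 | 13, 14 | none |
| Day 13 | 14 | none |
| Day 14 | none | none |
| Day 15 | none | 15 |
| Day 16 | none | 15, 16 |

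At the extremes the end of observation moves by 2/14 = 14% of the period. The same window at Day 28 means a Day 26 call leaves Days 27 and 28 unobserved for mortality by Day 28.

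**3. Consistency within the protocol.** Appendix 5 (Section 10.5.1) says, about interim cut-offs, that a participant followed for less than 14 days without progression has an unknown outcome and should not be counted as not progressed. A permitted Day 12 call creates the same situation. The missing-data text in Section 9.4.1 speaks of status on Day 14, which is a point status, whereas Section 9.4.2 asks whether participants "progress by at least one level higher on the modified WHO ordinal scale by Day 14".

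**4. The plan's sample size.** Inputs from Section 9.2: p1 = 0.30 (SOC), p2 = 0.15 (RESP301+SOC), one-sided alpha 0.025, 80% power, 2:1 allocation, N = 300. The usual two-proportion formula gives 88 controls (3 × 88 = 264). With continuity correction it gives 97 (3 × 97 = 291), within 3% of 300. The stated size is not in dispute.

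**5. Illustration of lost events.** The documents give no loss rate, so m = 5% and 10%, equal in both arms, are assumptions. The planned number of events is 0.30 × 100 = 30 and 0.15 × 200 = 30, so these rates mean 1.5 to 3 events lost per arm.

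Power = Φ[(d − c − 1.96·se0)/se1], where
- d = p1 − p2
- se0 = √[p̄(1 − p̄)(1/100 + 1/200)], with p̄ the pooled rate
- se1 = √[p1(1 − p1)/100 + p2(1 − p2)/200]
- c = 0 uncorrected, or ½(1/100 + 1/200) = 0.0075 with continuity correction.

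With no loss: p̄ = 0.20, se0 = 0.0490, se1 = 0.0523. Uncorrected, (0.15 − 0.0960)/0.0523 = 1.03, which gives 84.9%.

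| Events lost in each arm | Rates observed | Power, uncorrected | Power, corrected | Corrected N for 80% |
|---|---|---|---|---|
| 0% | 30% vs 15% | 84.9% | 81.3% | 291 |
| 5% | 28.5% vs 14.25% | 82.6% | 78.6% | 312 |
| 10% | 27% vs 13.5% | 80.1% | 75.7% | 333 |

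These are fixed-design figures and leave out the interim looks.

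**The case against.** **Daily scoring may run past Day 10.** The daily cell in the WHO row carries no day limit, while the laboratory cell in the same column is expressly limited to Days 3 and 7. Read alone, the column could mean scoring until discharge, and the inpatient gap would disappear. The column's place under the Intervention Period and before the Day 10 column points the other way. The text is ambiguous, and even on the generous reading the phone-call and window problems remain.

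**Much is still observed.** In-hospital worsening to Day 10, deaths by the time of contact, and worsening still present at contact are all found. A reader might infer that any readmission after discharge is lost. That goes too far: readmission to a study site before Day 11 falls in the daily column, and return on ordinary oxygen is level 4, which is no event for a level-4 entrant.

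**Safety reporting may help.** A reader might infer that there is no backstop, because Section 10.4.1 lists among events that are not AEs: "The disease/disorder being studied or expected progression, signs, or symptoms of the disease/disorder being studied, unless more severe than expected". The exclusion has that exception, and Section 10.4.2 makes hospitalization during safety follow-up of discharged participants a seriousness criterion. But the same section gives hospitalization for the disease under study as an example of what cannot be an SAE when it is not an AE, and nothing converts an AE record into a WHO level with a date. The backstop is partial.

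**Early withdrawal.** The WHO row has no mark in that column, and a reader might infer a further loss. It adds little: an inpatient who withdraws during treatment already has that day's reading.

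**Bias by arm.** The trial is open-label, so a reader might infer that contact days will be chosen by arm and inflate the false-positive rate. Nothing in the documents shows differential timing or loss.

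**Deferral to other documents.** Whether a Day 15 event counts is a derivation rule that an analysis plan could hold, and a look-back question could sit in a call script. The protocol nevertheless fixes what is scheduled and when contact may occur, so the collection gap belongs here.

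**Conclusion.** The concern holds in a limited form. The schedule captures most of the primary endpoint but not all of it. What is exposed is transient worsening on Days 11 to 13, readmission resolved before the call, and anything after an early contact. Worsening on Day 15 or 16 may be counted in error. The Days 11 to 13 part rests on reading the daily column as ending with the Intervention Period. The other parts rest on Section 8.1.1 meaning current status, since no look-back is specified.

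The structural size is 3 of 14 days (21%) for inpatients and up to 2 days (14%) from the window. The effect on results cannot be estimated from the documents. If 5 to 10% of events were lost equally in both arms, power would fall by about 2 to 5 percentage points uncorrected (84.9% to 82.6–80.1%), or 3 to 6 points with continuity correction (81.3% to 78.6–75.7%). That is a modest cost, and it falls on the primary endpoint. This should be fixed, but it does not invalidate the design.

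**What to change.** In Section 1.3 and Section 8.1.1:

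1. State that the WHO level is recorded daily from the chart while the participant is hospitalized, including any readmission, through Day 14.
2. At the Day 14 and Day 28 contacts, record the highest WHO level since the last assessment and the date it began, as well as current status.
3. Make the windows one-sided (Day 14 to Day 16, and Day 28 to Day 30). Count only progression dated on or before Day 14, and deaths on or before Day 28.

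The same dates would serve time to progression, which otherwise cannot be dated closely after Day 10. The cost is schedule wording, one or two case report form fields and one telephone question, with no added visit or procedure. The downside is some chart look-back, and contacts could no longer be made before the nominal day.
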